3.14.2. Patient Narratives	
3.14.3. Special Safety Top	pies30
3.14.4. Vital Signs	4-
3.14.5. Clinical Laborator	y Evaluation4:
3.15. Subgroup Analyses	40

I8F-MC-GPID Statistical Analysis Plan version 2

CONFIDENTIAL

3.1	5.1. Primary Efficacy Endpoints	46
3.1	5.2. Safety in Special Groups and Situations	47
3.16.	Interim Analyses and Data Monitoring Committee	48
4. U	Inblinding Plan	49
5. S	upporting Documentation	50
5.1.	Appendix 1: Kansas City Cardiomyopathy Questionnaire – Scoring Instructions	50
5.2.	Appendix 2: Search Criteria for Special Safety Topics	61
5.3.	Appendix 3: Cardiac Magnetic Resonance Imaging Substudy	64
5.4.	Appendix 4: Statistical Analysis for China	65
6. R	leferences	66

CONFIDENTIAL

I8F-MC-GPID Statistical Analysis Plan version 2

Table of Contents

Table		Page
Table GPID.3.1.	Description of Analysis Populations	13
Table GPID.3.2.	Baseline and Postbaseline Definitions for Safety Analyses	14
Table GPID.3.3.	Definition of Time-to-Event for a Specific Event of Interest	14
Table GPID.3.4.	Other Secondary	25
Table GPID.3.5.	Exploratory Efficacy Endpoints and Analyses	27
Table GPID.3.6.	Sample ADA Assay Results	36
Table GPID.3.7.	Sample Clinical ADA Interpretation Results	36
Table GPID.3.8.	In Silico Classification for Cross-Reactive NAb	37
Table GPID.3.9.	Adverse Events for Analysis with Immunogenicity Results	39
Table GPID.3.10.	Categorical Criteria for Abnormal Blood Pressure and Heart Rate Measurements	44
Table GPID.3.11.	Categorical Criteria for Additional Analyses of Heart Rate	45

CONFIDENTIAL

I8F-MC-GPID Statistical Analysis Plan version 2

Table of Contents

Figure		Page
Figure GPID.2.1.	Illustration of study design for Clinical Protocol I8F-MC-GPID	12
Figure GPID.3.1	Graphical testing scheme for Study GPID.	24
Figure GPID.3.2.	Flowchart of immunogenicity multitiered testing approach	35

Version history

This is the second version of the statistical analysis plan (SAP) for Study I8F-MC-GPID (GPID), which is based on Protocol (c) GPID, approved on 14 February 2024. SAP GPID version 1 was approved on 22 November 2021. See approval date for the current version of this SAP on Page 1.

Major Revision Summary for I8F-MC-GPID Statistical Analysis Plan Version 2

Section # and Name	Description of Change	Brief Rationale
Section 1.1 Primary Objective	change from baseline to Week 52 in the KCCQ-CSS, and occurrence of the composite endpoint of CV death and/or HF events over time.	To align with protocol (c).
	Hierarchical composite assessed by win ratio moved to other secondary endpoint.	
	Change from baseline to Week 52 in 6MWD moved to Key Secondary endpoints.	
Section 1.2 Key Secondary Objectives	Key secondary endpoints revised to	To align with protocol (c)
	 change from baseline to Week 52 in 6MWD percent change from baseline to Week 52 in body weight, and change from baseline to Week 52 in hsCRP. 	
	NYHA class, exercise capacity (6MWD at Week 24) moved from Key Secondary endpoints to Other Secondary endpoints.	

Section # and Name	Description of Change	Brief Rationale
Section 3.2 General consideration	Change end of study participation to end of follow-up. Add detail of time to event derivation.	To provide more details of the updated primary analysis and to align with the new primary endpoints.
Section 3.11.1 Study and Study Treatment Exposure	Included longer follow-up interval when summarizing duration.	To provide more details of exposure.
Section 3.11.2 Compliance to Study Treatment	Clarification of compliance criteria.	To align with protocol (c)
Section 3.13.1 Primary Endpoints/Estimands Analysis	Revised statistical methods related to primary endpoints.	To align with the revised primary endpoint and provide an appropriate analysis method for each endpoint/estimand.
Section 3.13.2 Key Secondary Endpoints/Estimands	Revised statistical methods related to key secondary endpoints.	To align with the revised primary endpoint and provide an appropriate analysis method for each endpoint/estimand.
Section 3.13.3 Type I Error Rate Control Strategy for Primary and Key Secondary Efficacy Analyses	Updated type I error rate control strategy	To provide details of the strategy.
Section 3.13.4 Other Secondary	 Other Secondary endpoints added including: hierarchical composite assessed by win ratio clinical outcome events of HF NYHA Class proportion of participants attaining ≥5%, ≥10%, ≥15% and ≥20% in body weight reduction change at Week 52 	To align with the revised primary endpoint and provide an appropriate analysis method for each endpoint/estimand.

Section # and Name	Description of Change	Brief Rationale
	 change from baseline to Week 24 in KCCQ-CSS added to other secondary endpoints proportion of participants attaining KCCQ-CSS MWPC threshold at Week 52 added to other secondary endpoints proportion of participants attaining ≥5 meters, ≥10 meters, and ≥15 points KCCQ-CSS change at Week 52 change from baseline to Week 24 in 6MWD proportion of participants attaining 6MWD meaningful within-patient change (MWPC) threshold at Week 52, and proportion of participants attaining ≥10 meters, ≥20 meters, and ≥30 meters 6MWD change at Week 52. 	
Section 3.13.5 Exploratory Endpoints	Exploratory endpoint "HF medication use" integrated into primary endpoint CV death and/or HF event. Clinical outcome events of HF	To align with the revised primary endpoint and provide an appropriate analysis method for each endpoint/estimand.
	moved to other secondary. Exploratory endpoint	
	"Evaluation of prespecified	

Section # and Name	Description of Change	Brief Rationale
	biomarkers" hsCRP; moved to key secondary endpoint.	
	Added exploratory endpoints:	
	 change from baseline to week 52 in waist to height ratio, and eGFR slope. 	
Section 3.14.3 Special Safety Topics	Added safety topics.	To align with PSAP GPID version 4.
Section 3.14.3.5.2 Liver Enzymes	Updated categorization.	To align with the new Lilly hepatic analyses plan.
Section 3.15 Subgroup Analysis	Updated categorization of subgroup variables. Removed subgroup of ARNi and age category of 75 and added new subgroups. Added safety in special groups and situations section.	To be consistent with baseline characteristics and to provide additional subgroups analysis. To align with PSAP GPID version 4 and provide submission level safety analyses details.
Section 5.1, Appendix 1	Added Kansas City Cardiomyopathy Questionnaire.	To provide details of the questionnaire.
Section 5.2, Appendix 2	Added further detailed search criteria for analysis of special safety topics.	To align with PSAP GPID version 4 and provide detailed descriptions of MedDRA search criteria.
Section 5.3, Appendix 3	Added additional endpoints of interest and analysis details.	To provide additional details of analysis for the cardiac MRI substudy.
Section 5.4, Appendix 4	Added statistical analysis for China.	To specify analyses to be performed for participants enrolled in mainland China and Taiwan.

Abbreviations: 6MWD = 6-minute walk test distance; ARNi = angiotensin receptor-neprilysin inhibitors; CV = cardiovascular; eGFR = estimated glomerular filtration rate; HF = heart failure; hsCRP = high-sensitivity C-reactive protein; KCCQ-CSS = Kansas City Cardiomyopathy Questionnaire-Clinical Summary Score; MedDRA = Medical Dictionary for Regulatory Activities; MWPC = meaningful within-patient change; NYHA = New York Heart Association; PSAP = program statistical analysis plan.

1. Study Objectives

1.1. Primary Objective

To demonstrate that a maximally tolerated dose (MTD) of tirzepatide up to 15 mg administered subcutaneously (SC) once weekly (QW) is superior to placebo in participants with heart failure (HF) with preserved ejection fraction (HFpEF) and body mass index (BMI) \geq 30 kg/m² based on:

- change from baseline in Kansas City Cardiomyopathy Questionnaire (KCCQ) Clinical Summary Score (CSS) at Week 52, and
- occurrence of the composite endpoint of cardiovascular (CV) death and/or heart failure (HF) events over time.

The effectiveness of tirzepatide will be demonstrated if either one or both the primary objectives is met. The details on type I error control are discussed in Section 3.13.3.

The HF event definition within Protocol GPID includes worsening symptoms or signs of HF, which are meaningful to the participant and require intensification of treatment characterized by one or more of the following: hospitalization for heart failure regardless of duration or treatment received; use of intravenous drug, usually an intravenous diuretic, but may include intravenous vasodilators or positive inotropic drugs; or augmentation or increase in oral diuretic therapy.

1.2. Key Secondary Objectives

[figure not shown]
The key secondary objectives are to demonstrate that tirzepatide MTD is superior to placebo with regards to

- change from baseline in 6-minute walk test distance (6MWD) at Week 52
- percent change from baseline in body weight at Week 52, and
- change from baseline in high-sensitivity C-reactive protein (hsCRP) at Week 52.

All the key secondary objectives are under multiplicity control. The details on type I error control are discussed in Section 3.13.3.

2. Study Design

Study GPID is a randomized, outpatient, multicenter, international, placebo-controlled, double-blinded, parallel arm Phase 3 study with 2 study periods. The study is designed to evaluate the efficacy and safety of QW tirzepatide MTD up to 15 mg compared to placebo in participants with HFpEF and BMI ≥30 kg/m². Figure GPID.2.1 illustrates the Study GPID design.

Note: Screening procedures may take longer or shorter than 6 weeks and variation in screening procedures will not be considered a protocol deviation.

Figure GPID.2.1. Illustration of study design for Clinical Protocol I8F-MC-GPID.

Two intervention groups will be studied:

- tirzepatide MTD up to 15 mg SC QW, and
- placebo.

Study GPID will compare treatment with tirzepatide and treatment with placebo. Assignment to tirzepatide or placebo groups will be randomly allocated in a 1:1 ratio.

The starting dose of tirzepatide is 2.5 mg QW, which will be escalated at 4-week intervals to a maximum of 15 mg QW, or to the highest maintenance dose tolerated by the participant.

The study will consist of 2 periods:

- Study Period 1: screening period, up to approximately 6 weeks, and
- Study Period 2: treatment period, with a 20-week escalation followed by at least a 32-week maintenance period.

Study GPID will continue until approximately 52 weeks after the last participant is randomized. The maximum duration of an individual's participation will depend on the duration of study enrollment.

3. A Priori Statistical Methods

3.1. Populations for Analyses

The populations for analyses are defined in the following table (Table GPID.3.1).

Table GPID.3.1. Description of Analysis Populations

Analysis Population	Description	
Entered	All participants who sign the ICF.	
Randomized/ITT Population	All participants assigned to treatment, regardless of whether they take any doses of study treatment, or if they took the correct treatment. Participants will be analyzed according to the treatment group to which they were assigned.	
Safety Population	All participants in the ITT population who take at least 1 dose of study treatment. Participants will be analyzed according to the treatment group to which they were assigned.	

Abbreviations: ICF = informed consent form; ITT = intent-to-treat.

3.2. General Considerations

Statistical analysis of this study will be the responsibility of Eli Lilly and Company or its designee. Some analyses and summaries described in this analysis plan may not be conducted if not warranted by data (for example, too few events to justify conducting an analysis). Additional analyses of the data may be conducted as deemed appropriate.

Statistical treatment comparisons will be performed between tirzepatide MTD and placebo. Unless otherwise specified, all tests of treatment effects will be conducted at a 2-sided alpha level of 0.05, and all confidence intervals (CIs) will be given at a 2-sided 95% level. Efficacy will be assessed using the intent-to-treat (ITT) population. Baseline is defined as the last nonmissing observation collected prior to or at randomization for efficacy analyses. Safety will be assessed using safety population and the definition of baseline and postbaseline for safety analyses are specified in Table GPID.3.2.

Analysis Type	Baseline	Postbaseline
1.1) Treatment-Emergent	The baseline period is defined as	Starts after the first dose of study treatment
Adverse Events	the start of screening and ends	and ends at the end of follow-up. See
	prior to the first dose of study	Section 3.2 for the definition of a participant's
	treatment (typically at Week 0).	end of follow-up.
1.2) Treatment-Emergent	Baseline will include all scheduled	Postbaseline will be defined as measurements
Abnormal Labsa and	and unscheduled measurements	after Visit 2. All scheduled and unscheduled
Vital Signs	during the baseline period (Visit 1	measurements will be included.
	and Visit 2).	
Analysis Type	Baseline	Postbaseline
1.3) Change from Last	The last scheduled and	Postbaseline will be defined as above (1.2).
Baseline to Week xx and	unscheduled nonmissing	Only scheduled visits will be included. The ET
to Last Postbaseline for	assessment recorded during the	visits are considered scheduled visits.
Labsa and Vital Signs	baseline period defined above	
	(1.2).	

Table GPID.3.2. Baseline and Postbaseline Definitions for Safety Analyses

Abbreviations: ET = early termination.

Summary descriptive statistics for continuous measures will include sample size, mean, standard deviation (SD), median, minimum, and maximum. Summary statistics for categorical measures (including categorized continuous measures) will include sample size, frequency, and percentages. Summary statistics for discrete count measures will include sample size, mean, SD, median, minimum, and maximum.

Unless otherwise specified, all observed data will be considered for analysis regardless of adherence to randomized treatment. The participant's end of follow-up will be the later of last contact date or study disposition date.

The definition of time-to-event for a specific event of interest is specified in Table GPID.3.3.

 Table GPID.3.3.
 Definition of Time-to-Event for a Specific Event of Interest

If a participant:	then:
Experiences the event	time-to-event for a specific event of interest will be the number of days
	between the date of randomization and the onset date of the event plus
	1 day.
Does not experience the event	the participant will be censored and the number of days between the
	date of randomization and the date of the participant's end of follow-up
	plus 1 day will be used for analysis.

Not all analyses described in SAP GPID will necessarily be included in the clinical study report (CSR). Any analysis described in this SAP and not provided in the CSR will be available upon request. Not all displays will necessarily be created as a "static" display. Some may be incorporated into interactive display tools instead of or in addition to a static display.

a Immunogenicity related analysis is specified in Section 3.14.3.8.

3.3. Adjustments for Covariates

The study is stratified by diagnosed type 2 diabetes mellitus (T2DM) (Y/N), HF decompensation (including hospitalization for HF requiring intravenous [IV] diuretic treatment or urgent HF visit requiring IV diuretic treatment) within 12 months of screening (Y/N), and baseline BMI group ($<35, \ge 35 \text{ kg/m}^2$). Unless otherwise specified, the stratification factors will be adjusted in the efficacy analyses. The value for stratification factors will be obtained from the data collected or derived from the electronic case report form (eCRF). In addition, the baseline value of the endpoint will be used as a covariate when appropriate.

3.4. Handling of Dropouts or Missing Data

For the primary and key secondary efficacy endpoint analyses subject to type I error rate control, missing data will be imputed based on the methods described in Section 3.13.1.3 and 3.13.2.

For all other endpoints, missing values will not be explicitly imputed unless specified otherwise.

3.5. Multicenter Studies

There is no stratification by site or country for randomization. However, the country or region effect may be examined for the primary endpoints through subgroup analysis.

3.6. Multiple Comparisons/Multiplicity

The type I error rate control strategy for primary and key secondary objectives is discussed in Section 3.13.3. There will be no multiplicity adjustments for evaluating other secondary and exploratory objectives and safety assessments.

3.7. Patient Disposition

Summaries and a listing of study disposition and study drug disposition will be provided for all randomized participants. Comparison between treatment arms will be performed using Fisher's exact test.

Summaries of study disposition will be provided for all entered but not randomized participants.

3.8. Historical Illnesses and Preexisting Conditions

The count and percentages of participants with historical illnesses and preexisting conditions will be summarized by treatment group using the Medical Dictionary for Regulatory Activities (MedDRA Version 27.0) preferred terms (PTs) nested within system organ class (SOC). The SOC will be in alphabetical order. Conditions (that is, PTs) will be ordered by decreasing frequency in tirzepatide MTD arm within SOC. This will be summarized for all randomized participants. Historical illnesses and preexisting conditions of special interest will also be summarized separately.

3.9. Patient Characteristics

A listing of participant demographics for all randomized participants will be provided. The demographic and baseline clinical characteristics will also be summarized by study treatment

group for all randomized participants. Baseline demographic and clinical characteristics of special interest include but are not limited to:

- age (years)
- sex (female, male)
- race
- ethnicity
- height (cm)
- weight (kg)
- BMI (kg/m^2)
- waist circumference (cm)
- age group $(<65, \ge 65; <75, \ge 75; <65, \ge 65 \text{ and } <75, \ge 75 \text{ and } <85, \ge 85)$
- BMI group (\ge 30 and <35, \ge 35 and <40, \ge 40 kg/ m²)
- country
- vital signs, and
- characterization of HFpEF and HFpEF-related comorbidities.

3.10. Concomitant Therapy

Concomitant medication will be summarized by treatment groups and displayed by decreasing frequency of WHODrug (Version MAR24B3) PTs in tirzepatide MTD arm.

In addition, medications of interest (as defined below) will be summarized by treatment groups:

- Baseline use of
 - o HF medications
 - o antihypertensive therapy other than HF medications
 - o antiplatelet and anticoagulant medications
 - o antihyperglycemic medications, and
 - o lipid lowering therapy.
- Changes to baseline medication post-randomization
 - o HF medications
 - o antihypertensive therapy other than HF medications
 - o antihyperglycemic therapy, and
 - o lipid lowering therapy.

3.11. Treatment Exposure and Compliance

3.11.1. Study and Study Treatment Exposure

A summary of duration on study follow-up (defined as time in days from date of randomization to the date of the end of follow-up plus 1 day) will be provided by treatment group in the ITT population.

A summary of duration on study treatment (defined as time in days from date of first dose of study treatment to date of last dose of study treatment plus 7 days) will be provided by treatment group in the safety population.

For the summary of duration on study and study treatment, the frequency and percentage of participants falling into the following categorical ranges will also be summarized by planned treatment group: >0 week, \geq 4 weeks, \geq 8 weeks, \geq 12 weeks, \geq 16 weeks, \geq 20 weeks, \geq 24 weeks, \geq 32 weeks, \geq 40 weeks, \geq 48 weeks, \geq 52 weeks, \geq 65 weeks, \geq 78 weeks, \geq 91 weeks, \geq 104 weeks, \geq 117 weeks, \geq 130 weeks, \geq 143 weeks, \geq 156 weeks.

In addition, the frequency and percentages of participants falling into the following exposure ranges for study and study treatment may be summarized by planned treatment group: >0 to <4 weeks, \geq 4 to <8 weeks, \geq 8 to <12 weeks, \geq 12 to <16 weeks, \geq 16 to <20 weeks, \geq 20 to <24 weeks, \geq 24 to <32 weeks, \geq 32 to <40 weeks, \geq 40 to <48 weeks, \geq 48 to <52 weeks, \geq 52 weeks to <65 weeks, \geq 65 weeks to <78 weeks, \geq 78 weeks to <91 weeks, \geq 91 weeks to <104 weeks, \geq 104 weeks to <117 weeks, \geq 117 weeks to <130 weeks, \geq 130 weeks to <143 weeks, \geq 143 weeks to <156 weeks, \geq 156 weeks.

No p-values will be reported in these summaries as they are intended to describe the study populations rather than test hypotheses.

3.11.2. Compliance to Study Treatment

A summary of prematurely discontinuing study treatment (including reason for discontinuation) will be provided by study treatment. A time-to-event analysis of premature study treatment discontinuation will also be conducted.

If the data warrants, the counts and percentages of participants who follow the planned escalation scheme, have dose interruption, or have dose modification, will be summarized for the tirzepatide-treated group. In addition, the proportion of participants receiving 2.5 mg, 5 mg, 7.5 mg, 10 mg, 12.5 mg, or 15 mg dose may be presented for the tirzepatide-treated group by visit during the dose escalation period.

Treatment compliance will be defined as taking at least 75% of the scheduled tirzepatide doses. Similarly, a participant will be considered significantly noncompliant if he or she is judged by the investigator to have intentionally or repeatedly taken more than the prescribed amount of medication (more than 125%).

Compliance over the whole treatment period will be calculated using the number of doses administered (regardless of the actual dose in mg administered) divided by the total number of doses expected to be administered ×100 over the treatment period. Total number of doses expected is defined as the number of weeks between the treatment end date and first dose date minus the number of dose interruptions due to adverse event (AE), investigator decision, or abnormal lab results if there are any. Treatment compliance will be summarized descriptively over the treatment period by treatment using the safety population.

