At Visit 2, prior to randomization, the participant needs to complete the 6MWT. Visit 2 may need to be conducted over 2 in-clinic visits (considered Visit 2a and Visit 2b) if a repeat 6MWT is necessary to assess participant eligibility. If the participant is required to return to repeat the 6MWT, the remaining procedures should be conducted at the second in-clinic visit for randomization (Visit 2b), more than 10 days from Visit 2a. See Section 10.10.1 for details on when a participant must return for a second Visit 2 6MWT.

Participants will be randomized and receive blinded study drug at the end of Visit 2 after all screening procedures are completed. The participant must not receive study drug until all eligibility criteria, including the 6MWT, are met.

Treatment

Starting from randomization, the participant receives study drug and procedures are conducted as described in the SoA (Section 1.3). Every effort should be made by the investigator to maintain participants on study drug.

Study drug dose will be escalated as illustrated in the study schema (Section 1.2). Dose escalation will continue until the participant reaches the maintenance dose of either 5 mg, 10 mg, or 15 mg. Participants who do not tolerate the first dose escalation (that is, from 2.5 mg to 5 mg [or placebo equivalent]) will need to discontinue from study drug.

Participants begin treatment with either tirzepatide or placebo starting at 2.5 mg given as a subcutaneous (SC) injection every week (QW). The dose level is increased by 2.5 mg increments approximately every 4 weeks for the first 20 weeks according to the participant's tolerability, reaching a MTD up to 15 mg. Once a MTD has been achieved, participants will continue at this MTD until study end, treatment discontinuation, or study discontinuation. Dose modifications will be permitted during the study under the circumstances specified in Section 6.6.

During the study treatment period, if an unscheduled visit or telephone visit is deemed necessary to support participant compliance, this is allowable at the discretion of the investigator site personnel. Optional telephone visits can be performed approximately 2 weeks after starting study drug and after each dose increase.

Participants will continue into the extended maintenance period with the same treatment assignment starting with Visit 13. Extended visits (EV) continue until criteria for study discontinuation is met or study ends (see Study Closeout and Final Visit below).

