6.4. Study Intervention Compliance

Participant compliance with study drug and adherence to study visits and procedures will be vitally important to meet the study objectives. This will be emphasized through comprehensive site training and consistently monitoring participant retention throughout the duration of the study.

Study drug compliance will be determined by the following:

• Study drug administration data will be recorded by the participants in the participant study diary and reviewed by the investigator at each study visit.

• The participants will be instructed to return any unused study drug and/or empty cartons at the next visit to the study site for the purpose of performing drug accountability.

Treatment compliance is defined as taking at least 75% of the required doses of study drug. Similarly, a participant will be considered significantly noncompliant if he or she is judged by the investigator to have intentionally or repeatedly taken more than the prescribed amount of medication (more than 125%).

In addition to the assessment of a participant's compliance with the study drug administration, other aspects of compliance with the study drug will be assessed at each visit based on the participant's adherence to the visit schedule, completion of study diaries, and any other parameters the investigator considers necessary.

Participants considered to be poorly compliant with their medication and/or the study procedures will receive additional training and instruction, as required, and will be reminded of the importance of complying with the protocol.

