6.6.2. Restarting Study Drug after Interruption

In certain situations, the investigator may need to temporarily interrupt study drug. Every effort should be made by the investigator to maintain participants on study drug and to restart study drug after any temporary interruption, as soon as it is safe to do so. Distribution of study drug at the correct dose will be per IWRS instructions.

If study drug interruption is	then
1 or 2 consecutive doses	Participant restarts study drug at last administered dose, per escalation schedule. If the participant has reached maintenance dose level, the study drug dose level will restart at the same prior achieved maintenance dose level.
3 or more consecutive doses	Participant restarts study drug (at 5 mg, managed by IWRS) and repeats dose escalation scheme until maintenance dose is reached. If maintenance dose has previously been established, the dose escalation cannot not exceed the prior achieved maintenance dose level.
Due to an AE	The event is to be documented and followed according to the procedures in Section 8.3.
Due to intolerable persistent GI AE	Participants should be treated as suggested in Section 6.5.

Abbreviations: AE = adverse event; GI = gastrointestinal; IWRS = interactive web response service.

Investigators should inform the sponsor that study drug has been temporarily interrupted.

Participants are not required to re-escalate to the prior maintenance dose level if a tolerability issue recurs during dose re-escalation.

If this attempted dose re-escalation to the prior maintenance dose level is not tolerated, the dose should be reduced to the next lower 5 mg incremental dose that was tolerated (for example, 5 mg or 10 mg). The participant will remain at that dose level for the duration of the study. During re-escalation after a temporary dose interruption, participants should be followed every 4 weeks until either a new lower maintenance dose level or prior maintenance dose level is reached.

For participants receiving 5 mg maintenance dose, no dose de-escalation is permitted. Only dose interruption is permitted to manage tolerability issues (Section 6.6.2). This can be performed through IWRS.

In the event that a participant has a temporary interruption that requires extending the escalation beyond Visit 8, unscheduled visits are allowed in the IWRS to facilitate a 4-week dispensing schedule to complete the escalation.

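### The SAP's expected-dose count subtracts the number of interruptions, not the doses withheld, so read literally it understates compliance after any multi-dose interruption

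*SAP*

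**What the plan says.** SAP 3.11.2 calculates compliance as "the number of doses administered (regardless of the actual dose in mg administered) divided by the total number of doses expected to be administered", times 100. It then defines the denominator in two parts, a week count less a deduction: "the number of weeks between the treatment end date and first dose date minus the number of dose interruptions due to adverse event (AE"). The deduction in full is "minus the number of dose interruptions due to adverse event (AE), investigator decision, or abnormal lab results if there are any". The threshold reads "Treatment compliance will be defined as taking at least 75% of the scheduled tirzepatide doses". The result is summarised descriptively, by treatment, in the safety population.

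The protocol's threshold is worded for both arms: "Treatment compliance is defined as taking at least 75% of the required doses of study drug" (Protocol 6.4).

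Dosing is weekly (Protocol 4.1). The restart table in Protocol 6.6.2 sorts interruptions by length: one row covers 1 or 2 consecutive doses and the next covers "3 or more consecutive doses". Protocol 6.6.1 has interruptions managed through the IWRS and entered on the eCRF, and tells sites not to record participant noncompliance as an interruption.

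SAP 3.11.2 does not define the treatment end date. SAP 3.11.1, just before it, measures time on treatment from the first dose to the last dose plus 7 days.

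**The concern.** The numerator and the week count are both in doses, or in weeks that stand for doses. The deduction is a number of interruptions. The two units agree only if every interruption lasts exactly one dose, and the protocol plans for longer ones.

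The deduction exists so that withholding for a medical reason does not count against the participant. As written, it protects one dose per episode and treats the remaining withheld doses as missed. That mixes interruption with noncompliance, which Protocol 6.6.1 keeps apart.

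At stake is a reported percentage with a fixed 75% cut-off. A participant who took every dose they were meant to take can be shown as non-compliant. In addition, because the treatment end date is undefined, two programmers could get different percentages from the same records.

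**Working it through.** The documents state no compliance figure, so there is nothing to reproduce. The check applies the SAP formula to a participant who takes every dose that was not withheld.

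**Inputs**
- *S*, scheduled weekly doses from first to last dose inclusive. *S* = 52 stands for the minimum 52-week treatment period (Protocol 1.1).
- *k*, doses withheld for an adverse event, investigator decision or laboratory result.
- *e*, number of interruptions; *e* = 1 here.
- *W*, weeks from first dose to treatment end. *W* = *S* if treatment end is last dose + 7 days (the SAP 3.11.1 convention). *W* = *S* − 1 if it is the last dose date.

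**Formulas**
- As written: 100 × (*S* − *k*) / (*W* − *e*).
- With withheld doses subtracted from scheduled doses: 100 × (*S* − *k*) / (*S* − *k*) = 100% for every *k*.

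**Results, S = 52, one interruption (none when k = 0)**

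| Withheld (*k*) | As written, end = last dose + 7 days | As written, end = last dose date |
|---|---|---|
| 0 | 52/52 = 100.0% | 52/51 = 102.0% |
| 1 | 51/51 = 100.0% | 51/50 = 102.0% |
| 2 | 50/51 = 98.0% | 50/50 = 100.0% |
| 4 | 48/51 = 94.1% | 48/50 = 96.0% |
| 8 | 44/51 = 86.3% | 44/50 = 88.0% |
| 13 | 39/51 = 76.5% | 39/50 = 78.0% |
| 14 | 38/51 = 74.5% | 38/50 = 76.0% |
| 15 | 37/51 = 72.5% | 37/50 = 74.0% |

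The 75% line is first crossed at 14 withheld doses under the +7-day convention and at 15 under the last-dose convention.

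**Other lengths of exposure**
- Longer: with *S* = 104 and the +7-day convention, the line is first crossed at *k* = 27, 77/103 = 74.8%.
- Shorter: with *S* = 8 and *k* = 3, the +7-day convention gives 5/7 = 71.4%, below the line. The last-dose convention gives 5/6 = 83.3%.

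**The week count on its own.** Under the +7-day convention it equals the dose count and is exact. Under the last-dose convention it is one dose short, in both arms, and raises compliance: 52/51 = 102.0%, or 4/3 = 133.3% for someone with only 4 doses. The two effects therefore have opposite signs, and figures from one convention should not be combined with figures from the other.

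**Average over an arm (assumed, since the documents give no interruption rates).** If 5% of an arm has one 2-dose interruption, mean compliance falls by 0.05 × 2.0 = 0.1 points. If 30% has one 8-dose interruption, it falls by 0.30 × 13.7 = 4.1 points. Both use *S* = 52 and the +7-day convention.

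**The case against.** The best defence is that the deduction was meant in doses. It sits inside a definition of expected doses, and Protocol 6.6.2 measures interruptions by the doses they cover. On that reading the formula works and only the wording is loose. This is possible, but the text says the number of interruptions, and the protocol treats an interruption as an episode with a length. A programmer following the sentence would count episodes, so it needs changing on either reading.

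Three stronger inferences are tempting, and the documents do not support them.

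- *Counting weeks is itself wrong.* That depends on the undefined end date. Under the SAP's own +7-day convention, used in 3.11.1 and for the on-treatment period in 3.13.1.4, the error is zero.
- *Perfect dosing could be labelled over-use.* The label in SAP 3.11.2 and Protocol 6.4 rests on the investigator judging that too much was taken intentionally or repeatedly, and it requires more than 125%. A denominator convention alone does not trigger it.
- *The formula makes tirzepatide look worse than placebo.* Protocol 6.5 names gastrointestinal events as the most common on tirzepatide, so more interruptions there are plausible. Neither document gives interruption rates or lengths by arm, so a difference can be neither established nor sized.

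It is also fair that long interruptions should be uncommon, because Protocol 6.6.1 and 6.6.2 ask for restart as soon as it is safe. The consequence is small too: there is no per-protocol population (Protocol 9.3, SAP 3.1), and the primary and key secondary analyses use all randomised participants under treatment policy (SAP 3.13).

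**Conclusion.** The point holds as a minor correction. Taken literally, the SAP 3.11.2 denominator understates compliance after an interruption of two or more doses when treatment end is last dose plus 7 days. Over 52 scheduled doses with one interruption, the shortfall is 2.0 points for 2 withheld doses, 5.9 for 4 and 13.7 for 8, and 14 puts a fully adherent participant under 75%. Short exposures are more sensitive.

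These sizes assume the +7-day end date, a single interruption and all other doses taken. If the end date is the last dose date, the shortfall is smaller and the 14-dose case stays above the threshold. The missing definition is a second, separate gap. No test, estimand or efficacy result depends on this percentage.

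**What to change.** Replace the denominator sentence in SAP 3.11.2 with one to this effect: expected doses are the scheduled weekly study-drug doses from first to last dose inclusive, (last dose date − first dose date)/7 + 1, minus the number of doses withheld within that span during interruptions for adverse event, investigator decision or abnormal laboratory results.

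- State the rounding, since Protocol 6.1 lets the dosing day move.
- This wording removes the need for a treatment end date. If the term is kept, define it.
- Write *study drug* in place of *tirzepatide* in the 75% rule, so that it matches Protocol 6.4 and covers placebo.

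The cost is a sentence or two in the SAP and a small programming change. Protocol 6.6.1 puts interruption data on the eCRF but does not list the fields, so confirm that the doses withheld can be counted from them. Participants also record the date of each dose in the diary (Protocol 6.1).
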